### **2.3.2 Entinostat (SNDX-275) induces *in vivo* inhibition of HST-S cells**

We validated three compounds in H-STS xenograft models in collaboration both with Champions Oncology and with the [name]'s lab at Columbia. These compounds included entinostat, tivantinib, and belinostat, predicted to have high, low, and negligible potency respectively in reverting activity of patient specific MR proteins. Assays from both labs confirmed that entinostat produced significant tumor size reduction over 25 days, while tivantinib had only a modest effect (40% viability reduction compared to DMSO, as predicted) and belinostat was indistinguishable from DMSO treated controls, also as predicted. Consistent with the analysis, entinostat activity was virtually identical at two different doses. From this analysis, considering that activity of the drugs was prioritized purely based on patient derived data and that cell line assays were used strictly to assess compound mechanism of action, in term of targeting critical MR proteins, we estimate that a minimum of 10% of GEP-NET patients should be highly sensitive to entinostat.

## **2.4 Dose Selection**

Entinostat has been evaluated *in vitro*, in nonclinical *in vivo* studies, and in Phase I and II studies in patients with various solid tumors and hematological malignancies at doses between 2 and 12 mg/m^2 and at dosing frequencies ranging from once daily to every 2 weeks. Increased histone acetylation was observed at the lowest dose evaluated with the effect persisting at least 48 hours post-dose. PK studies of entinostat have indicated a long half-life of entinostat, ranging from 40 hours to 120 hours. Consistent with this long half-life, entinostat concentrations were detectable 168 hours post-dose at doses of 2 to 12 mg/m^2.

The maximum tolerated dose (MTD) for single agent entinostat in non-hematologic indications was established as 4 mg/m^2 weekly × 3 and 1 week rest, or 10 mg/m^2 every other week continuously.

Pharmacokinetic analyses have demonstrated ~40% variability in the clearance of entinostat. However, when clearance was adjusted for body surface area (BSA), the inter-patient variability was similar. A linear regression analysis on factors that may contribute to this variability, such as ideal body weight, lean body mass, body weight, and body mass index, were not significant

covariates. As a result of this analysis, fixed dosing is considered to be as accurate as dosing based on BSA ([Alao 2004](#)). Entinostat given once weekly continuously at a dose of 5 mg (in combination with the aromatase inhibitor exemestane) in a clinical study in patients with locally advanced or metastatic breast cancer and given every other week continuously at a dose of 10 mg (in combination with erlotinib) in patients with stage IIIB/IV NSCLC was well tolerated. Entinostat's AE profile at these dose schedules was consistent with previous clinical experience, with the most common AEs being fatigue and gastrointestinal disturbances, (nausea, vomiting, and diarrhea).

## **2.5 Scientific Hypothesis**

[figure not shown]
It is hypothesized that entinostat will:

- inhibit proliferation of a subset of abdominal neuroendocrine tumors with a signature transcriptional interactome
- arrest tumor progression as evidenced by tumor shrinkage or stabilization in the study patient population.

## **3. EXPERIMENTAL PLAN**

### **3.1 Study Design**

This is an open-label, single arm, multi-center Phase II trial of entinostat given as a 5 mg oral dose every week (days 1, 8, 15, and 22 of a 4-week cycle) in patients with relapsed or refractory abdominal neuroendocrine tumors. Patients will continue on treatment until disease progression or intolerable toxicity occurs.

### 3.2 Number of Centers

Up to 4 study centers in the US will be recruited for participation in the study.

### 3.3 Number of Patients

Up to 40 patients with relapsed or refractory abdominal neuroendocrine tumors may be enrolled to achieve up to 32 response-evaluable patients. Safety will be evaluated in an ongoing fashion. It is anticipated that no more than 25% of enrolled patients will be non-evaluable for response.

## 4. PATIENT ELIGIBILITY

### 4.1 Inclusion Criteria

Patients must fulfill all of the following inclusion criteria in order to be admitted into the study:

1. Pathologically confirmed stage IV unresectable relapsed, or unresectable refractory abdominal neuroendocrine tumor from the last biopsy available which may be the initial diagnostic biopsy.  
Relapsed disease is defined as progressive disease following systematic therapy with lanreotide or equivalent. Refractory disease is defined as disease not responding to or having progressed within 1 month of the last dose of most recent systemic therapy to include lanreotide or an analog. (Note, small cell carcinoma and large cell undifferentiated neuroendocrine tumors will be excluded from this trial).
2. Eligibility for stage 2 of the study, if the extension stage is opened, will be determined by RNAseq analysis and master regulator profile of a single fresh needle biopsy specimen obtained during study screening.
3. Documented disease that is radiographically measurable.
4. Last dose of prior therapy must be > 14 days before the first dose of study drug administration. There is no upper limit to number of prior therapies. However, the patient must have recovered from acute toxicities from the most recent therapy to grade 1 or less.
5. ECOG performance status of 0 or 1 (must be done within 7 days prior to study drug administration).
6. Age 18 years or older
7. Total Bilirubin  $\leq 1.5 \times$  Upper Limit of Normal (ULN) and AST and ALT  $\leq 2.5 \times$  ULN (results within 7 days before study drug administration),  $\leq 5 \times$  ULN for patients with liver metastases.
8. Serum creatinine  $\leq 1.5 \times$  ULN (results within 7 days before study drug administration)
9. Absolute neutrophil counts of  $\geq 1500/\mu\text{L}$  (without growth factor support), platelet counts  $\geq 100,000/\mu\text{L}$  (without transfusion support); and hemoglobin  $\geq 9$  g/dL results within 7 days before study drug administration.
10. Patients or their legal representative must be able to read, understand, and sign a written informed consent
11. International Normalized Ratio (INR) or Prothrombin Time (PT)  $\leq 1.5 \times$  ULN unless patient is receiving anticoagulant therapy as long as PT or PTT is within therapeutic range of intended use of anticoagulants AND Activated Partial Thromboplastin Time (aPTT)  $\leq 1.5 \times$  ULN unless patient is receiving anticoagulant therapy as long as PT or PTT is within therapeutic range of intended use of anticoagulants
12. If a female of childbearing potential, has a negative serum blood pregnancy test during screening and a negative urine pregnancy test within 3 days prior to receiving the first dose of study drug. If the screening serum test is done within 3 days prior to receiving the first dose of study drug, a urine test is not required. Note: Women of childbearing potential (WoCP) are any women between menarche and menopause who have not been permanently or surgically sterilized and are capable of procreation. Permanent sterilization includes hysterectomy and/or bilateral oophorectomy and/or bilateral salpingectomy but excludes bilateral tubal occlusion. WoCP include non-women who have experienced menopause onset < 12 months prior to enrollment.
13. If a female of childbearing potential, willing to use 2 methods of birth control or willing to abstain from heterosexual activity for the course of the study through 120 days after the last dose of study drug.
14. If male, agrees to use an adequate method of contraception starting with the first dose of study drug through 120 days after the last dose of study drug.

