## **8. CORRELATIVE STUDIES**

### **Biomarker Evaluations**

#### **8.1 Tissue Sampling**

A requirement of phase 2 protocol entry is the presence of a metastatic focus accessible to biopsy. All patients who enter the second phase of the trial that would require a specific gene expression profile for eligibility will be asked to undergo a single image-guided fine-needle biopsy. For patients in the first part of the protocol who agree, a minimum of 0.05mg of fresh metastatic tissue (a single needle core biopsy) will be obtained prior to treatment initiation for RNAseq and master regulator analysis. If the protocol extends to the second part, all patients

will be required to undergo biopsy in order to establish eligibility for the second part of the study if it is initiated.

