### **11.3 Sample Size Considerations**

#### **11.3.1 Initial Protocol**

Up to 40 patients may be enrolled to achieve 32 response-evaluable patients. It's anticipated that no more than 25% of enrolled patients will be non-evaluable for response.

The sample size for the expansion phase is based on a Simon 2-stage design (optimum version) and objective response rate endpoint described in Section 11.2. To calculate the required sample size, the following assumptions were made. The response probability of an ineffective therapy in this indication (i.e., the uninteresting response level) was chosen to be 15%; the response probability of an effective therapy (i.e., the targeted response level) was chosen to be at least 35%, level of significance of 10%, and power of 80%. Based on these

assumptions, the sample size of the first and second stage is 9 and 14, respectively, for a total of 23 response-evaluable patients (see below).

- If less than 2 of the 9 patients achieve an objective response (CR or PR) during the first stage of the study, enrollment will be terminated for unselected patients and entinostat will be declared to have insufficient activity in this indication in unselected patients. Thereafter, enrollment will be restricted to patients whose tumors display the characteristic master regulator expression profile consistent with hypothesized entinostat sensitivity.
- If 6 or more unselected patients achieve objective response after completion of the second stage, then entinostat will be considered sufficiently promising in this treatment setting and may be evaluated in future studies.
- If the total number of patients with objective response after completion of the second stage is between 2 and 5, further development of entinostat in this indication will be assessed. If the true objective response rate for entinostat is  $\leq 15\%$ , then the expected sample size is 14.61 patients, with probability of terminating the study at the end of the first stage equal to 60%.

Up to 40 patients may be enrolled to achieve 32 response-evaluable patients (9 unselected patients in stage 1, and 23 selected patients in stage 1 and 2).

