#### **11.4 Interim Analysis and Early Stopping Guidelines**

An interim analysis is planned after enrollment in Stage 1 is complete and the primary efficacy endpoint is determined for all response-evaluable patients who are enrolled in stage 1 based on the first 6 cycles of protocol therapy. A patient is considered response-evaluable if they meet the criteria described for the per-protocol population in Section 11.5. Based on the continuation criterion described in Section 11.3, enrollment will either continue into stage 2 or will be limited to patients whose tumors display the correct master regulator profile consistent with sensitivity to entinostat.

Safety will be assessed in an ongoing fashion based on the incidence of adverse events, serious adverse events, and treatment discontinuations due to adverse event. No formal safety stopping rules are specified. However, if any significant safety issues arise, a decision to modify or terminate the trial will be made.

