## APPENDIX 1: SCHEDULE OF STUDY ASSESSMENTS

Assessments	Screening	Cycle 1				Even Cycles (2,4,6, etc.)		Odd Cycles (3,5,7, etc)		EOT	Safety F/up
		D 1 +/- 3 days	D 8 +/- 3 days	D 15 +/- 3 days	D22 +/- 3 days	D1 +/- 3 days	D15  +/- 3 days	D1 +/- 3 days	D15  +/- 3 days		
Informed consent	X										
Medical History & Medications	X 										
Physical exam, vitals, weight, Performance status (ECOG)	X	X 	X 	X 	X 	X 	X 	X 	X 	X	X
Hematology and Blood chemistry tests	X 	X 		X 		X 	X 	X 	X 	X 	X
Urinalysis	X									X	
Thyroid functions: TSH, T3, T4	X									X	
Serum pregnancy test (WOCBP only)	X										
12-lead ECG	X									X	X 
Disease assessment / contrast CT and octreotide scan	X 							X 		X 	
Clinical Disease Assessment	X	X	X	X		X	X	X	X	X	
Tumor Biopsy (if archival tissue not available)	X										
Adverse events / concomitant medication information collection		X	X	X	X	X	X	X	X	X	X
Entinostat compliance assessment		X	X	X	X	X	X	X	X	X	
Entinostat drug administration		X	X	X	X	X	X	X	X		
Long Term Telephone Contact 											

Note all medications taken within 28 days of C1D1

Only a symptom directed physical exam is required at these visits.

Hematology: CBC with differential, platelets, RBC, HGB, HCT; Blood chemistry: ALT, AST, alkaline phosphatase, albumin, total bilirubin, BUN, calcium, creatinine, electrolytes (sodium, potassium, magnesium {only at screening unless clinically indicated}, chloride, bicarbonate), glucose, LDH, phosphorus, total protein, uric acid.

performed only if one was not done within 28 days prior to C1D1; Octreotide scan required only at screening.

Follow-up scans must include the area of interest, the prospectively selected indicator lesion(s); the same method used at baseline should be used for all serial measurements. Required every 3 cycles.

Performed only if disease progression was not previously documented

ECG required if new abnormality is observed during study and not resolved at EOT.

Following patient termination from study, every 2 months until disease progression and every 3 months after disease progression for overall survival

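### Inclusion criterion 2 makes the biomarker profile the entry test for stage 2 without limiting it to the route after stage 1 fails, while the statistics section counts unselected patients in stage 2

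*Combined protocol and SAP*

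**What the plan says.** **Eligibility.** Criterion 2, worded alike in the synopsis and in section 4.1, reads: "Eligibility for stage 2 of the study, if the extension stage is opened, will be determined by RNAseq analysis and master regulator profile". The specimen is to be a fresh needle biopsy taken at screening. The criterion stands in a list whose items must all be met. The term extension stage is not defined anywhere.

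**Tissue sampling.** Section 8.1 says that, should the protocol be extended, every patient "will be required to undergo biopsy in order to establish eligibility for the second part of the study if it is initiated". Earlier in the same paragraph it describes the second phase as one in which an expression profile decides entry.

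**Statistics.** Section 11.3.1, like the synopsis, restricts enrollment to profile-positive patients only when fewer than 2 of the 9 stage 1 patients respond. Its success rule begins: "If 6 or more unselected patients achieve objective response after completion of the second stage". Section 11.4 says that after the interim analysis "enrollment will either continue into stage 2 or will be limited to patients whose tumors display the correct master regulator profile", so stage 2 is there the alternative to selection. The last line of section 11.3.1 then divides the 32 evaluable patients into 9 unselected in stage 1 and 23 selected across stages 1 and 2.

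**Procedures.** The Appendix 1 row is headed "Tumor Biopsy (if archival tissue not available"), in line with section 7.1, which asks for archival tissue first.

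**The concern.** Stage 2, second part and extension stage are used for two different cohorts: the remaining 14 unselected patients after stage 1 passes, and the selected patients enrolled after it fails. Criterion 2 does not say which it means, and section 11.4 uses stage 2 for the branch that criterion 2 appears to exclude.

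The final decision depends on the answer. If stage 1 passes and criterion 2 is enforced as worded, the next 14 patients are profile-positive. There are then only 9 unselected patients for a rule designed for 23, or else two populations are pooled in a test that describes neither. Enrolling the wrong stage 2 population cannot be repaired in the analysis.

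**Working it through.** **Inputs (section 11.3.1).** Uninteresting rate 15%; target rate 35%; level 10%; power 80%; optimal Simon design; n1 = 9, n2 = 14, total 23; continue if at least 2 of 9 respond; promising if at least 6 respond in total. Stated properties at a true rate of 15%: expected sample size 14.61, probability of early stopping 60%.

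**Formula.** With response rate a in stage 1 and b in stage 2,

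R(a, b) = sum over x = 2 to 9 of Bin(x; 9, a) × P(Y ≥ 6 − x), where Y is binomial(14, b).

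**Step 1: reproduce the plan, one population in both stages.**
- Early stopping at 15%: 0.85^9 + 9 × 0.15 × 0.85^8 = 0.2316 + 0.3679 = 0.5995 (stated 60%).
- Expected size: 9 + 14 × (1 − 0.5995) = 14.61 (as stated).
- Level: R(0.15, 0.15) = 0.2597 × 0.1465 + 0.1069 × 0.3521 + 0.0283 × 0.6433 + 0.0050 × 0.8972 + 0.0006 = 0.0990 (stated 10%).
- Power: R(0.35, 0.35) = 0.8037 (stated 80%).

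All four figures agree, so the arithmetic is sound for a single population.

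**Step 2: when the conflict matters.** It reaches the unselected rule only if stage 1 passes. That probability is 1 − 0.5995 = 0.40 at a 15% rate and 1 − 0.1211 = 0.88 at 35%.

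**Step 3: criterion 2 taken literally, only unselected responders counted.** Six responders must come from 9 patients. At 35%: 0.0424 + 0.0098 + 0.0013 + 0.0001 = 0.0536. At 15%: 0.0006.

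**Step 4: criterion 2 taken literally, all 23 counted.** The unselected rate is held at 15%, the uninteresting level. The documents give no response rate for selected patients, so the rates in the first column below the first row are assumptions.

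| Stage 2 rate | Terms for x = 2, 3, 4, 5, ≥ 6 | Chance of promising |
|---|---|---|
| 15% (no difference) | as in step 1 | 0.099 |
| 25% | 0.1243 + 0.0769 + 0.0254 + 0.0049 + 0.0006 | 0.232 |
| 35% | 0.2024 + 0.0979 + 0.0277 + 0.0050 + 0.0006 | 0.334 |
| 50% | 0.2522 + 0.1062 + 0.0283 + 0.0050 + 0.0006 | 0.392 |

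The result cannot exceed 0.40, because stage 1 must first pass on unselected patients.

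**The case against.** The best defence is that the intent can be recovered. The synopsis and sections 11.3.1 and 11.4 consistently place selection after stage 1 failure. Criterion 2 is conditional on an extension stage being opened, and the description of the second phase in section 8.1 can be read as limiting the biopsy to the cohort that needs a profile. The last line of section 11.3.1 gives selected patients their own stages 1 and 2, and 9 + 23 = 32 fits that reading exactly. This stands as an account of the likely intent. It does not remove the conflict, because criterion 2 names stage 2 with no such limit and the conditional term has no definition.

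Three stronger readings are tempting, and the documents do not support them.
- A reader might infer that the 6-of-23 decision cannot be carried out at all. It can, on the coherent reading just given.
- A reader might infer that Appendix 1 sets up another definition of stage 2. Its biopsy row concerns screening tissue, matches section 7.1 and says nothing about stage 2 entry. What is missing there is a line for the fresh biopsy.
- A reader might take 5.4% or 33% as the trial's actual power or error rate. The first applies a rule meant for 23 patients to 9. The second counts selected patients under a rule that names unselected ones, at an assumed response rate.

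It is also unknown how sites would apply criterion 2. Registration relies on an eligibility checklist that is not among the documents.

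**Conclusion.** The concern holds as an internal inconsistency about which population enters stage 2. The Simon figures are correct, but the 10% level and 80% power apply only if unselected patients fill both stages. Criterion 2, followed literally after stage 1 passes, would prevent that.

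The probabilities in steps 3 and 4 are conditional scenarios. They assume literal enforcement of criterion 2, and step 4 also assumes the selected response rates. The inflation appears at each selected rate tried above 15%. The branch in question is the more likely one if the drug works (0.88 at a 35% rate), so the wording should be settled before any patient is enrolled beyond stage 1.

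**What to change.** 1. In the synopsis and section 4.1, limit criterion 2 to the selected cohort opened after fewer than 2 of 9 unselected responses. Limit section 8.1 in the same way.
2. State that stage 2 of the unselected cohort has no profile requirement.
3. Name the cohorts separately, for example Cohort U stages 1 and 2 and Cohort S stages 1 and 2. Use the names throughout, including the last line of section 11.3.1, in place of second part and extension stage.
4. State that the two cohorts are never pooled for the 2-of-9 or 6-of-23 counts.
5. Align the biopsy text in both section 7.1 and Appendix 1 with the fresh biopsy already required for the selected cohort.

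The cost is amendment wording. Sample size and thresholds stay as they are, and no procedure is added beyond the biopsy that criterion 2 and section 8.1 already call for.

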## 4.2 Exclusion Criteria

Patients fulfilling any of the following criteria will not be admitted into the study:

1. Patients with another active cancer (excluding basal cell carcinoma or cervical intraepithelial neoplasia [CIN / cervical carcinoma in situ] or melanoma in situ). Prior history of other cancer is allowed, as long as there is no active disease within the prior 5 years.
2. Pregnant or lactating women. Women of child-bearing potential (WOCBP) must have a negative serum pregnancy test documented within 3 days prior to start of study drug.
3. Patients with uncontrolled intercurrent illness, active or uncontrolled infections, or a fever  $>38.5^{\circ}\text{C}$  that has not been evaluated for infection up to the day of initial dosing. Patients with documented history of tumor fever are accepted provided acute or chronic infection has been excluded as possible cause of the fever.
4. Patients who have been treated with any investigational drug within 28 days prior to the first dose of study medication, or who are receiving concurrent treatment with other experimental drugs or anti-cancer therapy.
5. Prior treatment with HDAC inhibitors (e.g. valproic acid, Zolinza® (SAHA), romidepsin (Istodax®).
6. History of pericarditis or pericardial effusion that had required medical or surgical intervention in the last 6 months, or myocardial infarction or arterial thromboembolic events within 6 months, or experiencing severe or unstable angina, or New York Heart Association (NYHA) Class III or IV disease, or a QTc interval  $>0.47$  seconds
7. Known HIV or a history of active Hepatitis B or C as evidenced by laboratory abnormalities in addition to positive serology. Testing is not required for patients not suspected of having these conditions
8. Any condition (e.g., known or suspected poor compliance, psychological instability, geographical location, etc) that, in the judgment of the investigator, may affect the patient's ability to sign the informed consent and comply with study procedures
9. Any condition that will put the patient at undue risk or discomfort as a result of adherence to study procedures
10. Presence or history of brain metastases.
11. Uncontrolled hypertension or diabetes mellitus
12. Any contraindication to oral agents or significant nausea and vomiting, malabsorption, or significant small bowel resection that, in the opinion of the investigator, would preclude adequate absorption.
13. Allergy to benzamide or inactive components of entinostat.
14. Patients may not be taking any corticosteroid for any reason while on study and all corticosteroids must be stopped two weeks prior to initiation of study drug.

